Tart Cherry Juice for Sleep in Older Adults with Insomnia: A Pilot Study of Feasibility and Comprehensive Mechanisms (CherryZZZ)

Study Protocol
IRB# Pro00078791
NCT #06786494

CHAPTER 1. INTRODUCTION

[figure not shown]
Preliminary studies have shown that drinking tart cherry juice daily can help increase sleep quantity in older adults with insomnia. This study aims to corroborate previous findings, determine study feasibility, and generate preliminary data on several putative corresponding mechanisms on how tart cherry juice may impact sleep. It is planned as a randomized, double-blind, placebo-controlled, cross-over intervention in 20 older adults with self-reported insomnia. After daily consumption of tart cherry juice and placebo (each for 4 weeks), change in sleep quantity/quality and relevant biomarkers (e.g., melatonin, cortisol, serotonin, and inflammatory makers) will be measured.

CHAPTER 2. BACKGROUND

An alarming 40-70% of older adults are estimated to have chronic sleep problems, which consequently increases risk of detrimental health outcomes, including physical ailments, mental health issues, and cognitive decline.¹ Although effective, pharmacological strategies are often paired with severe adverse effects, which dissuade older adults from seeking treatment and leave them suffering from poor sleep.² Thus, there is an urgent need to identify safe, non-pharmacological strategies that optimize sleep to maintain healthy aging in older adults and avoid the adverse outcomes often resulting from poor sleep.

Diet offers a safe, non-pharmacological strategy to modulate sleep. Two small pilot studies in older adults with insomnia (i.e., a condition marked by poor sleep) report that intake of tart cherry juice for 2 weeks increased sleep quantity (e.g., total sleep time), but not quality (e.g., patient-reported satisfaction with sleep).^{3,4} Poor sleep quality is associated with mortality and other diseases of aging,⁵⁻⁸ which underscores the importance of improving both sleep quantity and quality. Interventions targeting improved sleep quality typically have durations of at least 4 weeks as previously reviewed.⁹ Given that the previous studies had 2-week durations of tart cherry juice intake, longer studies may be required to see increases in both sleep quantity and quality.

Despite 2 successful pilot studies that show tart cherry juice increases sleep quantity in older adults, the underlying mechanisms remain unclear. Tart cherry juice is made from a specific type of cherry variety that is uniquely concentrated with **melatonin**, an important compound involved with the initiation of sleep.¹⁰ Yet, there are also other factors in tart cherries that may impact sleep,¹¹⁻¹⁵ including: **tryptophan**, a precursor to serotonin, a mood regulating hormone,¹⁵⁻¹⁸ **magnesium**, a micronutrient that regulates the production of cortisol, a stress hormone,^{19,20} and **flavonoids**, plant-based compounds that protect cells from damage and lower inflammation in the body (**Figure 1**).^{11,13} Cherry-derived melatonin, tryptophan, magnesium, and

flavonoids all have specific effects on biomarkers, which consequently have downstream effects on sleep-associated factors (i.e., **reduction in core body temperature**,^{10,21,22} **improved mood**,^{18,23-25} **reduced stress**,²⁶⁻²⁸ **and reduced pain**,²⁹⁻³¹ respectively). Clarification of the mechanisms underlying the impact of tart cherry juice on sleep will allow us to ultimately identify other potential foods and/or dietary patterns that provide similar compounds to help with sleep.

CHAPTER 3: RESEARCH DESIGN

3.1 Study Objectives and Aims

The **overall goal** of this study is to determine feasibility of a tart cherry juice intervention in older adults, and generate preliminary data of outcomes and mechanisms related to sleep. We propose a 2-arm randomized, double-blind, cross-over study in 20 older adults with self-reported insomnia. Participants will consume 240 mL of tart cherry juice or placebo (calorically matched to the tart cherry juice beverage, but theoretically devoid of melatonin, tryptophan, magnesium and flavonoids), twice/evening for approximately 4 weeks in a randomly assigned order. The aims are:

Aim 1: Determine the feasibility of recruiting individuals for and implementing a 4 week tart cherry juice intervention in older adults with self-reported insomnia. Hypothesis: Recruitment for and implementation of a tart cherry juice intervention in older adults with self-reported insomnia is feasible.

Aim 2: Generate preliminary data for sleep quantity, sleep quality, and relevant biomarkers in older adults with self-reported insomnia enrolled in a double-blind randomized placebo controlled tart cherry juice intervention. Hypothesis: Intake of tart cherry juice tends to increase sleep quantity (via sleep monitoring device), sleep quality (via validated questionnaire, e.g., the Pittsburg Sleep Quality Index) urinary melatonin, and serum serotonin, as well as decrease urinary cortisol and serum inflammatory markers.

Exploratory Aim: Explore the impact of tart cherry juice intake on sleep-related factors that may be impacted by the Aim 2 biomarkers in older adults. Hypothesis: Intake of tart cherry juice for 4 weeks results in changes in mood, stress, and pain.

3.2 Overview

This will be an individual-level, 2-arm, randomized, cross-over pilot in 20 older adults with self-reported insomnia to determine feasibility of a tart cherry juice intervention and to generate preliminary data on measures of sleep and related biomarkers needed to plan a future trial. Participants will complete a 1-week (approximately 7 nights of sleep) pre-intervention assessment of sleep quantity, since several nights of data are needed to reduce variation in these outcomes. They will be randomized to consume tart cherry juice or placebo, which is nutritionally matched to the cherry juice beverage, but without significant amounts of our putative active cherry compounds (e.g., melatonin, tryptophan, magnesium, or flavonoids). They will be asked to consume their assigned intervention in the evening: 240 mL (i.e., 8 ounces) at approximately 5 pm and 240 mL (i.e., 8 ounces) at approximately 1 hour before bedtime for 4 weeks. After approximately 2 weeks of washout, they will repeat the same process with the other arm of the study (**Figure 2**).

[figure not shown]

Figure 2. Proposed Cross-over Pilot Study Design. Eligible participants will consume either tart cherry juice or placebo for 4 weeks in a randomized order. Before each arm, individuals will have a one week assessment of sleep via wearable device (e.g., Garmin watch™). Blood and urine for biomarkers will be assessed before and after each arm of the intervention, while questionnaire based assessments will be administered before, during, and after each arm. After a two-week washout period, participants will be asked repeat the same process with the other arm.

3.3 Inclusion and Exclusion Criteria

Our target population is older adults, with self-reported insomnia. Individuals expressing an interest in participating will be screened to confirm that they meet the following inclusion and exclusion criteria.

Inclusion Criteria

- Men and women aged ≥ 65 years
- Self-reporting insomnia (e.g., trouble sleeping approximately 3 nights a week for at least 6 months and/or an Insomnia Severity Index score ≥ 10 points³²)
- Usual bed-time between 8:00 pm and 1:00 am

Exclusion Criteria

- Unwilling to follow the study protocol
- Inability to properly use the wearable device, complete smartphone-based surveys, or follow the intervention protocol
- Self-report of medically diagnosed sleep disorders except insomnia (e.g., sleep apnea)
- Current and consistent use of sleep aids or hypnotic prescriptions (e.g., trazadone)*
- Self-report of cognitive impairment, dementia, or other neurological disorder
- Are on unstable medications (i.e., change within the last 3 months) for other conditions
- Have an allergy to the intervention products
- Self-report history of diabetes
- Current alcohol (Alcohol Use Disorders Identification Test ≥ 4 points^{33,34}) or drug use disorder (Drug Abuse Screening Test,^{35,36} DAST-10 > 2 points)
- Are excessive caffeine drinkers (≥ 5 cups of caffeinated beverages a day)
- Any other reason/condition the PI and investigative team believe this intervention would be unsafe

*If individuals currently use certain sleep aids (e.g., melatonin), but are willing and able to avoid their use during the study, participants will be asked to avoid the use of the sleep aid for approximately 2-3 weeks before continuing with the study.

3.4 Number of Subjects and Study Duration

We aim to recruit a total of 20 individuals (both men and women) through local newspaper and internet advertisements, physician referrals, our registry of research volunteers, Hebrew SeniorLife (HSL) senior housing sites, and patient registries (e.g., HRC or Beth Israel Deaconess Medical Center). Given that a primary goal of this study is to determine recruitment and attrition rate, we may not have exactly 20 individuals who complete the study. Participants will remain in the study for a total of approximately 12 weeks.

3.5 Study Endpoints

The primary outcome is feasibility. Secondary outcomes are sleep quantity, sleep quality, and select biomarkers. Exploratory outcomes include mood, stress, pain. See §6.2 for further information.

3.6 Study Intervention Products

Tart cherry juice will be purchased from a commercial supplier (e.g., Shoreline Fruit™). Shoreline Fruit will be responsible for preparing and bottling the tart cherry juice. Frozen or fresh tart cherries will be juiced and bottled according to the manufacturers normal processing. The intervention products will be prepared following proper food safety/handling protocols and the bottles. The bottles of tart cherry juice will be labeled with a letter, number or symbol, that distinguishes it from the placebo.

Unsweetened black cherry powder (e.g., Kool-aid™) will be purchased and used as the placebo. A reputable, established lab (e.g., Rutgers Food Innovation Center) will prepare the placebo, who will follow safe, good manufacturing practices. The placebo will be prepared to match the caloric/sugar content of the tart cherry juice. The Kool-aid has a similar taste and color, however does not contain significant amounts of our active ingredient (i.e., tart cherries) or active putative compounds (e.g., magnesium, melatonin, tryptophan, flavonoids). The placebo will be bottled in the same bottle type that the tart cherry juice is bottled in, however it will be marked with a letter, number, or symbol that differs from the one used to identify the tart cherry juice.

The key that decodes which of the letter/number corresponds with which product will be kept secure by an independent party (e.g., an individual at the Biostatistics and Data Sciences Core of the Marcus Institute). Thus, the participants, study staff, and analyzers of the data will be blinded to the letter/number that is used to identify the tart cherry juice vs the placebo. At the end of the data collection and data analysis, the study team will be unblinded. See §5.3 for further information on dietary intervention. Individuals will be provided with an allotment of the intervention products and additional bottles will be delivered by our study staff as needed.

CHAPTER 4 RECRUITMENT AND DATA COLLECTION

4.1 Recruitment Overview

Participants will be recruited from the Boston area community, including senior housing facilities in urban/suburban areas and research recruitment repositories. We will utilize a multi-pronged approach to meet our recruitment goals:

- We will recruit from the research repository that resides at HRC
- We will connect with social workers in and outside the HRC
- We will perform medical record reviews to identify potentially eligible individuals at the Hebrew SeniorLife (HSL) geriatric medicine practices.
- We will advertise through direct mailings to all residents of HRC's seven supportive housing facilities (over 3,000 residents).
- We will give presentations at Hebrew SeniorLife (HSL) facilities.
- We will use the Harvard Catalyst (CTSA) and Shared Health Research Information Network (SHRINE) to identify volunteers from Harvard-affiliated hospitals and clinics.
- We will advertise our study within numerous local media outlets, on HRC's Hinda and Arthur Marcus Institute for Aging Research and other websites (e.g., Craig's List and targeted web-based advertisements via BuildClinical), and at www.clinicaltrials.gov.

4.2 Recruitment Timeline and Randomization

Our trial proposes to enroll 20 individuals over approximately 6-months. In an attempt to account for the impact of order, we will randomly assign individuals to the order in which they receive the intervention and placebo. For example some individuals will start with the intervention and then placebo, others will start with the placebo and then the intervention. This process will be carried out while maintaining participant and investigator blinding. Block randomization will be employed as a means to reduce the impact of season/time.

4.3 Informed Consent

All interested individuals will be asked to provide verbal consent to complete an initial eligibility screen during a phone conversation with study personnel. Potentially eligible participants will then schedule an in-person screening visit. Potential participants may be sent by email or conventional post (per request, and according to their preference) a copy of the informed consent form for them to review at their own pace prior to the in-person screening. Written informed consent will be obtained by trained study personnel at the beginning of the in-person screening visit.

4.4 Participant Withdrawal

Any participant who expresses a desire to discontinue participation in the study will be withdrawn at their request immediately. All data collected prior to withdrawal will be maintained in the study data set.

Additionally, a participant may be withdrawn from the study prior to completing all of the study related procedures due to the following conditions:

- Participant safety issues
- Failure of subject to adhere to protocol requirements (including low compliance with the intervention)
- Disease progression
- Participant decision to withdraw from the study (withdrawal of consent)

Withdrawn participants may not reenter the study unless there are extenuating circumstances (e.g. family emergency or required travel out of town) that interfere with the start of the study before any interventions are administered. In this case, they may be scheduled to start over again. If new medical conditions arise or are exacerbated during the study intervention, the withdrawal of a participant will be evaluated by the PI.

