Compliance: Compliance with our dietary intervention will be evaluated throughout the study. Participants will be asked to log consumption of their juice and keep all of their empty bottles. Participants will return all remaining empty/full bottles to estimate number of intended doses that were consumed.

Within the first 5 days of starting each intervention arm, participants will be called to confirm there is no impact of the timing of juice impact on sleep quality. If a participant discloses that they are noticing lower than usual sleep quality after consuming the juice, the timing of the dose will be modified to mitigate any negative effects.

Week 3 and Week 10 (~30 minutes): These visits may take place over the phone. They will include an evaluation of relevant symptoms, related sleep factors, depressive symptoms, stress, pain, and compliance. Participants will be asked to fill out a 3-day diet record to estimate nutrient intake in the week prior to their next visit.

Related Sleep Factors: In addition to the assessment of sleep quality and quantity, we will also collected data about factors that are known to affect sleep (e.g., use of alcohol, room temperature via sensor given to participants), that may occur to help characterize or understand unexpected/unusual patterns in the data.

Week 5 and Week 12 Visits (~60 minutes): Participants will be asked to turn in their 3-day diet records. Relevant symptoms, weight, vitals, sleep quality, related sleep factors, depressive symptoms, stress, pain and any additional relevant questionnaires will be evaluated. Additionally, up to 16 mL of blood will be taken to measure biomarkers in serum and a morning urine sample will be collected.

At Week 7, participants will be asked to fill out a 3-day diet record to estimate nutrient intake in the week prior to their next visit. This is not an official visit.

At the end of the intervention (e.g., Week 12 Visit), participants will be asked to provide feedback via open ended questions on their experience during the intervention. They will also be asked if they would be willing to consume this intervention long-term and to guess as to which arm they were on in the beginning and ending of the intervention.

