5.4 Outcome Measures

Our primary endpoints are aspects of feasibility. Secondary endpoints include sleep quantity and quality, as well as sleep-related biomarkers (e.g., melatonin, serotonin, cortisol, inflammatory markers). Exploratory outcomes include sleep-related factors (e.g., mood, stress, pain). We will also explore other alternative outcomes.

Name	Type	Timeframe	Brief description
Recruitment Rate	Primary	Throughout the entire study	Number of individuals that need to be screened to be enrolled that are randomized to the intervention.
Attrition	Primary	Throughout the entire study	Number of individuals randomized that withdraw from the intervention in media res .
Compliance of Dose	Primary	Throughout the entire study	The number of intended doses consumed.
Ability to Collect Data	Primary	Throughout the entire study	The percentage of missing data points from electronic capture data devices.
Practicality	Primary	Throughout the entire study	Self-reported willingness to continue the dietary regimen after study completion.
Sleep Quantity	Secondary	Throughout the entire study	Individuals will be asked to wear a polysomnographic device (e.g., Garmin

			watch) to continuously measure aspects related to sleep quantity (e.g., total sleep time, time spent awake).
Sleep Quality	Secondary	Week 1, 5, 8, 12	The validated self-report questionnaire, the Pittsburgh Sleep Quality Index, which ranges from 0-21 points.
Melatonin	Secondary	Week 1, 5, 8, 12	Melatonin will be estimated by measuring the major urinary metabolite of melatonin, 6-sulphatoxymelatonin, utilizing a commercially available quantitative immunoassay.
Serotonin	Secondary	Week 1, 5, 8, 12	Serotonin production will be estimated by measuring the kynurenine/tryptophan ratio in blood collected from participants utilizing a commercially available quantitative immunoassay.
Cortisol	Secondary	Week 1, 5, 8, 12	Urinary cortisol will be estimated utilizing a commercially available quantitative immunoassay.
Inflammatory Markers	Secondary	Week 1, 5, 8, 12	A panel of several serum biomarkers related to inflammation (e.g., C-reactive protein, interleukin-6) will be measured in blood collected from participants utilizing a commercially available quantitative immunoassay.
Mood	Exploratory	Week 1, 3, 5, 8, 10, 12	A validated self-report questionnaire (e.g., the CES-D/CESD R, which ranges from 0-60 points or the PHQ-9, which ranges from 0-27 points)

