6.1 Statistical Analysis

All analyses will be performed by intent to treat, and further evaluated per protocol. As a first step, we will assess distribution characteristics of the primary and secondary outcomes. Where appropriate, transformation of variables to combat skew or other irregularities will be employed. Participant characteristics will be summarized using means, medians, standard deviations, interquartile regions and ranges for continuous variables and sample counts and proportions generated for discrete characteristics. Comparability of treatment arms will be assessed on potentially confounding characteristics using tabular and graphical methods.

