6.2 Outcome Variables

Below are the specific outcome variables planned for the study.

Primary Endpoints

Study feasibility is evaluated by several identified measures listed in §5.4, however others will be explored. Feasibility outcomes will be summarized using sample quantities and corresponding 80% confidence interval estimates. The specific thresholds that will determine study feasibility will be fully described in the manual of procedures.

Secondary Endpoints

Sleep quantity will be captured via a device that has polysomnographic capacity (e.g., Garmin Watch™), which continuously measures quantitative aspects of sleep (e.g., total sleep time, number of awakenings, wake time after sleep onset, etc.). The sleep diary that a participant logs their time in bed and time out of bed will help us correct any issues with the objective measures. The primary aspect of sleep quantity will be total sleep time, however others will be explored. Participants will be asked to wear the device all day and night during the study. Change in measures of sleep quantity will be calculated between baseline and midpoint, as well as baseline and final follow-up visit. The distribution of change in sleep quantity scores will be summarized using means and standard deviations or medians and interquartile ranges, as appropriate. We will develop 80% confidence interval estimates of inter- and intra- individual variation (i.e., standard deviation) of change in these measures.

Sleep quality will be measured by a validated self-report questionnaire: the Pittsburgh Sleep Quality Index (range: 0-21),³⁸ where higher scores indicate worse sleep. Change in sleep quality scores will be calculated between baseline and final follow-up visit. The distribution of change in sleep quality scores will be using means and standard deviations or medians and interquartile ranges, as appropriate. We will develop 80% confidence interval estimates of inter- and intra-individual variation (i.e., standard deviation) of change in these measures.

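### Section 4.4 lets staff withdraw participants from the study for low compliance, which blurs the two primary outcomes of compliance and attrition and ends follow-up of the participants Aim 1 most needs to observe

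*Combined protocol and SAP*

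**What the plan says.** Section 4.4 first covers withdrawal at the participant's request and adds that "All data collected prior to withdrawal will be maintained in the study data set". It then says that "a participant may be withdrawn from the study prior to completing all of the study related procedures due to the following conditions", and one of the conditions is "Failure of subject to adhere to protocol requirements (including low compliance with the intervention". The section gives no cut-off, timing or decision procedure for low compliance. Re-entry is generally barred; the exception concerns interruptions before any product has been given.

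Section 5.4 names both affected quantities as primary outcomes. Compliance of dose is "The number of intended doses consumed", and attrition is "Number of individuals randomized that withdraw from the intervention" partway through. Section 3.4 also calls the attrition rate a primary goal. Section 5.2 describes how doses are counted, from a log and from bottles: "Participants will return all remaining empty/full bottles to estimate number of intended doses that were consumed".

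On analysis, section 6.1 states: "All analyses will be performed by intent to treat, and further evaluated per protocol". Section 6.3 makes Aim 1 a descriptive tabulation and Aim 2 a paired t-test of change on juice against change on placebo. The feasibility limits are held elsewhere: "The specific thresholds that will determine study feasibility will be fully described in the manual of procedures".

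**The concern.** Low compliance is both a result to be measured and a ground for ceasing to measure it. In a study that asks whether older adults will drink the product every evening for 4 weeks, the person who will not is among the most informative participants.

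Withdrawing that person has four consequences:

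- A compliance result becomes an attrition event, and the timing and number of such events depend on staff judgement.
- Later compliance, including in the second arm, is never observed.
- The question on willingness to continue, which section 5.2 places at the end of the study (for example at Week 12) and section 5.4 lists as the primary outcome of practicality, may not be asked of those plausibly least willing.
- A participant withdrawn in the first arm has no second-period change and cannot enter the paired Aim 2 test. Section 8.6 plans to design later trials from the variation in change seen here, so that variation would come disproportionately from compliers.

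The outcome definitions do not settle how such a person is counted. Section 5.4 does not say whether withdrawal by staff counts as attrition, and it gives compliance no denominator once someone has left.

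**Working it through.** The plan states no expected compliance or attrition figure, so there is nothing to reproduce. The example below shows how far the reported figures depend on the rule and on the unstated denominator.

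**From the documents.** The target is 20 participants (section 3.4), with two doses per day for about 4 weeks in each of two arms (sections 3.2 and 5.2). Taking 4 weeks as 28 days, scheduled doses per person are 2 × 28 × 2 = 112.

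**Assumed.** Three of 20 take 40% of their doses and the other 17 take 90%. The three are withdrawn at day 14 of the first arm, about the time of the Week 3 contact. By then each has had 2 × 14 = 28 doses due and has taken 0.4 × 28 = 11.2. Each of the other 17 takes 0.9 × 112 = 100.8.

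**Compliance with no withdrawals**

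(17 × 0.9 + 3 × 0.4) / 20 = 16.5 / 20 = 82.5%

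**Compliance with the three withdrawn.** Doses taken are 17 × 100.8 + 3 × 11.2 = 1,747.2.

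| Denominator | Calculation | Compliance |
|---|---|---|
| All scheduled doses, all randomized | 1,747.2 / (20 × 112) = 1,747.2 / 2,240 | 78.0% |
| Mean of each person's on-study percentage | (17 × 0.9 + 3 × 0.4) / 20 | 82.5% |
| Pooled doses due while on study | 1,747.2 / (3 × 28 + 17 × 112) = 1,747.2 / 1,988 | 87.9% |
| Completers only | 0.9 | 90.0% |

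**Attrition.** If staff withdrawals do not count, it is 0/20 = 0% (exact 80% interval 0 to 10.9%). If they count, it is 3/20 = 15% (5.6% to 30.4%). Each such withdrawal moves attrition by 1/20 = 5 points. The 80% level is the one section 6.2 sets for feasibility outcomes.

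**Range.** With 1 to 6 low compliers taking 20% to 60% of doses:

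- no withdrawals: 69.0% to 88.5%
- withdrawn, all scheduled doses: 64.5% to 86.3%
- withdrawn, pooled on-study doses: 83.2% to 89.6%
- withdrawn, completers only: 90%

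**Aim 2.** In the example, at most 20 − 3 = 17 complete pairs remain. Sections 6.1 to 6.3 describe no method for missing data, so keeping pre-withdrawal data does not supply the missing half of a pair.

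**The case against.** A reader might infer that the rule removes the failures from both primary outcomes and makes the compliance threshold easier to pass. The documents do not support that. The rule is permissive, data gathered before withdrawal are kept, intent to treat comes first, and attrition is defined over randomized individuals. Section 4.4 treats staff and participant withdrawals under one heading, so the natural reading is that a withdrawn low complier counts as attrition. The failure then appears in another primary outcome, at 5 points each. Nor is the direction for compliance fixed: of the four denominators, two inflate it, one leaves it at 82.5% and one lowers it to 78.0%. All of this stands.

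Two further points stand in part. Any early leaver, for whatever reason, lacks a complete pair for Aim 2, so that loss is not peculiar to this rule; but here the plan itself adds to it, and does so selectively. The Manual of Procedures, which is not available here, may hold a compliance cut-off or counting rule. That could settle the counting, but it would not restore observations lost when a participant is taken out of the study.

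It can also be said that a descriptive 20-person pilot needs no more than clearer definitions. Definitions would fix the denominators. They would not recover later compliance, the willingness answer or the second-period change.

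**Conclusion.** The concern holds in a limited form. Followed as written, section 4.4 allows staff discretion to convert compliance results into attrition and to cut short observation of low compliers, which sits badly with the primary outcomes in section 5.4 and with intent to treat in section 6.1. Failures are relabelled or truncated; they are not necessarily hidden.

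In the 3-of-20 example, identical drinking behaviour gives compliance anywhere from 78.0% to 90.0%, a spread of 12 points, and attrition of 0% or 15%. The number of low compliers, their dose rates and the day of withdrawal are assumptions. The example also supposes that every low complier is withdrawn, which the rule permits but does not require. Whether any feasibility threshold would be crossed cannot be judged without the Manual of Procedures.

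**What to change.** Reconcile section 4.4 with sections 5.4 and 6.1 so that low compliance alone does not end scheduled data collection. Safety withdrawal, the participant's right to leave, and any decision about continuing or stopping product stay outside this change.

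In section 5.4:

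- Compute compliance over all scheduled doses for all randomized participants.
- Compute attrition over all randomized participants, counting investigator-initiated and participant-initiated withdrawals alike.
- Report the two kinds of withdrawal separately, by product and period.

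The cost is protocol wording and a few continued visits. The feasibility figures may look slightly less favourable than under a completers-only or on-study count. The change should be made before anyone is withdrawn under the rule, because observations lost that way cannot be recovered.
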